#### *Minimally invasive diagnostic work-up*

Pan-enteric CE is performed at the center from which the patient is included. Before CE, patients are evaluated for small bowel patency with a thorough clinical assessment, supplemented with the patency capsule system if deemed necessary. Assessment of small bowel patency can be supplemented with IUS prior to examination with the patency capsule in centers with experience in this procedure. If bowel patency is confirmed, pan-enteric CE is performed using standard bowel preparation as described below. If bowel patency is not confirmed, the patient will cross over to a standard diagnostic work-up with IC plus MRE. If the capsule fails to pass from the stomach to the duodenum during the examination, the procedure will be considered failed and the patient will cross over to a standard diagnostic work-up. Endoscopic delivery of the capsule to the duodenum is not permitted in this study.

CE is analyzed by central reading performed by an expert reader and lesions of interest are confirmed and countersigned by a second expert. In case of disagreement between the first and second expert on findings or clinical recommendation after the examination, an evaluation committee of several expert readers will provide a final decision. Results are reported standardized as described below, and the treating

gastroenterologist is provided with the result. Decisions regarding diagnosis, additional diagnostic work-up and treatment are made afterwards by the treating physician.

[figure not shown]
#### *Standard diagnostic work-up*

Patients go through a diagnostic work-up in accordance with international guidelines including IC with segmental biopsies plus a small bowel examination, either MRE or SBCE as selected by the investigating clinician. MRE is preferred in patients with suspected complications to CD (stenosis, abscess or fistula). CE is preferred in patients without disease complications. Patients are scheduled for IC at one of the participating centers using standard bowel preparation and sedation according to local preferences. MREs and SBCEs are performed locally at the participating centers. Results are reported in a standardized fashion. After completing all diagnostic procedures, the treating gastroenterologist is provided with the results of IC and MRE or SBCE, and decisions regarding diagnosis, additional diagnostic work-up and treatment are made.

#### *Follow-up*

Patients are followed clinically for 12 months according to the result of the initial diagnostic work-up:

- **Non-IBD:** Patients are interviewed by the primary investigator or the study nurse after 12 months.
- **IBD:** Data are collected 3, 6, 9 and 12 months after diagnostic work-up.

#### **Artificial intelligence**

Parallel to the standard review of pan-enteric CEs, a secondary AI-supported review will be conducted. Full-length anonymized videos will be processed and reviewed in a cloud-based deep learning solution such as AXARO (Augmented Endoscopy, Paris, France). Results are reported in a standardized fashion and compared to the standard review. In cases with disagreement between standard review and AI-assisted review, findings

are presented to an IBD expert with experience in CE not involved in the standard or AI review for classification of lesions, diagnosis, severity, localization, and need for additional diagnostic work-up.

## Treatment

After completing all bowel examinations, a final diagnosis is made. Patients are discharged (non-IBD) or followed in the gastroenterology outpatient clinics by the treating physician. Additional examinations, medical or surgical treatment are performed without restrictions.

## Blood tests

Prior to inclusion in the study, the following blood tests are performed in accordance with the standard clinical praxis for newly referred patients: Hemoglobin, erythrocyte volume fraction, platelet count, total and differential leukocyte count, C-reactive protein, sodium, potassium, albumin, creatinine, alanine aminotransferase, alkaline phosphatase, bilirubin, thyrotropin (TSH), transglutaminase IgA, total IgA or deamidated gliadin IgG, ferritin, cobalamin and folate.

## Stool samples

Stool samples are examined by polymerase chain reaction for pathogenic bacteria and intestinal parasites, and fecal calprotectin is measured as a part of routine clinical praxis.

## Biobank

A biobank is not included in this study.

## Number of patients

We aim to include 165 patients in the study.

## Time perspective

Inclusion in the study begins 1st of September 2024 and ends 1st of April 2027. Clinical follow-up will continue until 1st of September 2027.

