## Endpoints

*Primary endpoint:*

1. Diagnostic completeness, defined as the proportion of patients in each group achieving a complete gastrointestinal assessment and an unambiguous diagnosis after the first-line work-up strategy without need for supplementary examinations.

*Secondary endpoints:*

1. Feasibility of pan-enteric CE: Number of patients with suspected CD examined with pan-enteric CE and the number of ICs avoided
2. Additional examinations: Need for additional examinations in the two randomization arms
3. Safety: Number of severe adverse events, delayed or missed diagnoses
4. Time to diagnosis: Time from referral or first diagnostic procedure to a final diagnosis and treatment
5. Disease classification and medical treatments in the two randomization arms
6. Patient satisfaction: Difference in Gastrointestinal Endoscopy Satisfaction Questionnaire (GESQ) score
7. Costs: Expenditure on diagnostic procedures, treatment and loss of productivity
8. Artificial intelligence: Diagnostic utility of AI algorithms in detection of gastrointestinal pathology using pan-enteric CE – sensitivity, specificity, severity, prediction and impact on clinical decision making

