## **Information from medical records**

*Transmission without consent*

Before the patient has signed the declaration of consent, information including personal data from referrals to participating centers will be passed on to the investigators in order to determine eligibility for inclusion as per the in- and exclusion criteria mentioned above. Referrals marked with a diagnosis code listed in appendix 1 can be passed on to the investigators. Personal data passed on comprises name, Central Personal Register (CPR) number, and the referral text which may include symptoms, physical findings, medications, preexisting conditions, and results from previously performed biochemical and imaging examinations. We expect to screen 330 referrals during the inclusion period from September 1st 2024 to April 1st 2027.

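### Every patient is to be followed for 12 months, but clinical follow-up closes 153 days after inclusion ends, so patients included after 1 September 2026 cannot complete it

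*Protocol*

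**What the plan says.** Protocol, Follow-up, sets one length for everyone: "Patients are followed clinically for 12 months according to the result of the initial diagnostic work-up". The content then differs by diagnosis. For IBD: "Data are collected 3, 6, 9 and 12 months after diagnostic work-up". For non-IBD there is one contact: "Patients are interviewed by the primary investigator or the study nurse after 12 months".

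Protocol, Time perspective, fixes the calendar: "Inclusion in the study begins 1 st of September 2024 and ends 1 st of April 2027", and then "Clinical follow-up will continue until 1 st of September 2027". Information from medical records repeats the inclusion dates: "We expect to screen 330 referrals during the inclusion period from September 1 st 2024 to April 1 st 2027". The end of inclusion is therefore stated twice and the end of follow-up once.

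The Treatment section describes what happens after the final diagnosis: "Patients are discharged (non-IBD) or followed in the gastroenterology outpatient clinics by the treating physician". Among the secondary endpoints is "Safety: Number of severe adverse events, delayed or missed diagnoses"; treatments and costs are listed there too. No section sets a common cut-off date or a reduced follow-up for patients who enter late.

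**The concern.** Both statements concern clinical follow-up, so they cannot be read as describing different activities, and on the stated dates they cannot both be met for patients included late.

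A late non-IBD patient would miss the only follow-up contact that is scheduled for this group, after having been discharged. That interview is the protocol's planned check on whether a negative work-up missed disease. A late IBD patient would lose month 12 and, with later entry, possibly months 9 and 6. Delayed or missed diagnoses, treatments and costs would then be counted over shorter periods for late entrants than for early ones. A statistical analysis plan can say how to handle incomplete follow-up, but it cannot supply contacts that the study calendar rules out.

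**Working it through.** **Inputs.** Inclusion 1 September 2024 to 1 April 2027 and end of follow-up 1 September 2027 (Time perspective); 12 months of follow-up with the contacts above (Follow-up); 165 patients (Number of patients); CD in 39% and 43% of patients in two earlier studies (Statistical considerations).

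**Assumptions, not in the protocol.** Uniform accrual; 31 to 91 days from inclusion to completed work-up; the CD share standing in for the IBD share. IBD also includes other diagnoses, so the true share may be higher.

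**Step 1: can the stated end date be reproduced?** Last inclusion plus 12 months = 1 April 2028. The protocol states 1 September 2027, which is 213 days (7 months) earlier. Starting the clock at the work-up widens the gap.

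**Step 2: the cut-off.**
- 1 April to 1 September 2027 = 153 days of possible follow-up for the last patient. An IBD patient has 153 − 31 = 122 or 153 − 91 = 62 days after work-up.
- 1 September 2027 minus 12 months = 1 September 2026, the latest inclusion date that allows month 12 with the clock at inclusion.
- The inclusion window is 942 days, of which the last 212 fall after that date: 212/942 = 22.5%.

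**Step 3: patients who cannot reach month 12 under uniform accrual.**

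| Clock | Calculation | Patients of 165 |
|---|---|---|
| Inclusion, all patients | 212/942 × 165 | 37.1 |
| Work-up for IBD only, 31 days | 0.61 × 37.1 + 0.39 × 42.6 to 0.57 × 37.1 + 0.43 × 42.6 | 39.2 to 39.5 |
| Work-up for IBD only, 91 days | 0.61 × 37.1 + 0.39 × 53.1 to 0.57 × 37.1 + 0.43 × 53.1 | 43.3 to 44.0 |
| Work-up, all patients, 31 days | 243/942 × 165 | 42.6 |
| Work-up, all patients, 91 days | 303/942 × 165 | 53.1 |

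The Follow-up section times visits from the work-up explicitly only for IBD. For the non-IBD interview it names no starting point, so the middle rows follow its wording most closely. If accrual finishes by 1 September 2026 (clock at inclusion), or earlier by the work-up time, the number is 0.

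**Step 4: earlier visits, IBD patients only.** Even with the clock at inclusion, month 9 falls too late for those included after 1 December 2026 (the last 121 days) and month 6 for those included after 1 March 2027 (the last 31 days). Counting from the work-up brings both dates forward.

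**The case against.** The strongest reply is that the consequence is limited and conditional. The primary endpoint is settled after the first-line work-up. The Endpoints section sets no time window for the secondary endpoints concerned. Medical records are a data source under Transmission with consent, so some events may be recovered without a contact. If recruitment finishes early enough, nobody is affected. All of this stands, and it limits the weight of the point. It does not reconcile the dates: the protocol plans inclusion to 1 April 2027 and says so twice, and it does not say that record review continues after follow-up closes.

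A reader might infer three stronger things that the protocol does not support:

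- **Bias between the arms.** Allocation is concurrent and stratified by center, so late entry shortens follow-up in both arms. Nothing shows that it does so differently.
- **Patients left without care.** IBD patients stay in the outpatient clinics, and the Treatment section leaves further examinations and treatment unrestricted. What is lost is study data.
- **Non-IBD patients with no study contact at all.** They still have the baseline visit, the procedures and the satisfaction questionnaire. Only the scheduled follow-up contact is lost.

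**Conclusion.** The contradiction holds and should be fixed. The 153 days and the 1 September 2026 cut-off follow from the stated dates alone. The patient counts do not: about 37 of 165 needs uniform accrual with the clock at inclusion; about 39 to 44 adds an assumed 31- to 91-day work-up and an IBD share of 39 to 43%; about 43 to 53 needs every patient timed from the work-up. These are illustrations of size, not forecasts, because the protocol gives no accrual curve. Reading them as a known loss of a fifth or more of the patients would go too far.

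The damage is confined to secondary endpoints that depend on follow-up, which would be observed over unequal periods. How much each endpoint changes cannot be calculated from the protocol. The primary endpoint and the sample size of 165 stand.

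**What to change.** In Time perspective, replace the fixed end date with 12 months after the last included patient's diagnostic work-up, which is not before 1 April 2028 if inclusion ends as stated. Add that the primary endpoint may be analyzed earlier and the 12-month endpoints after that date. Follow-up and Information from medical records can then stand as they are.

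**Cost.** One date amendment, a later 12-month report, and at least 7 more months of contacts that are already planned (8 to 10 months with a 1- to 3-month work-up). Coordinator time depends on how the post is charged. The budget gives 400,000 DKK, as 2 years at 200,000 DKK, while the stated calendar is 36 months. Pro rata, 400,000/36 × 7 to 10 months = about 78,000 to 111,000 DKK. At the annual rate, 200,000/12 × 7 to 10 months = about 117,000 to 167,000 DKK.

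**Alternatives.** Closing inclusion by 1 September 2026 (earlier by the work-up time) would also reconcile the dates, but at the planned average pace it includes only about 730/942 × 165 = 128 patients. A declared common cut-off with a minimum follow-up would remove the contradiction on paper without restoring the lost contacts.

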## Statistical considerations

The diagnostic completeness of pan-enteric CE and conventional diagnostic work-up depends on the chosen inclusion criteria, severity of lesions and disease location. In two previous studies performed by our group with similar inclusion criteria, CD was diagnosed in 43% and 39% of patients, respectively. The following performance measures were derived:

- *Drop out:* Pan-enteric CE was not performed in 10% of patients because of suspected small bowel stricture, patient demands or unwillingness to complete the procedure.
- *Complete procedures:* A complete IC and pan-enteric CE was achieved in 86% and 82% of patients, respectively. MR-enterography was not completed in accordance with the protocol in 1-5% of patients.
- *Diagnostic performance:* The sensitivity of CE for diagnosing CD in the terminal ileum was significantly higher compared to MR (100% vs 81%). The diagnostic yield of CE for detection of CD in the proximal small bowel was also higher compared to MR (15-22% vs. 3%). The sensitivity of CE for diagnosing CD in the colon was 75% compared to IC.

### *Expected diagnostic completeness*

Minimally invasive diagnostic work-up: With 10% of patients withdrawn from the procedure, 80% complete examinations and a diagnostic procedure in 90%, the expected diagnostic completeness of pan-enteric CE is 65%.

Standard diagnostic work-up: With 5% of patients withdrawn from at least one of the procedures, 90% complete examinations and diagnostic procedures in 90%, the expected diagnostic completeness of pan-enteric IC plus MR enterography or SBCE is 77%.

### *Sample size calculation*

In a randomized controlled non-inferiority trial with a 2:1 ratio of patients examined with CE and standard diagnostic procedures (IC + MR enterography or SBCE), significance level 0.05, power 0.8, expected diagnostic completeness in samples 0.65, expected diagnostic completeness in controls 0.77 and a margin on risk difference scale 0.3, the following number of patients are required to show non-inferiority between two diagnostic strategies: 165 (110 in CE arm and 55 controls).

## **Data capture and randomization**

Data are collected and stored in a secured REDCap database under OPEN (Open Patient data Explorative Network). REDCap also provides a tool for 2:1 randomization of patients for minimally invasive diagnosis or standard diagnostic work-up, respectively.

The additional AI-assisted review, will act as another layer of safety in CE – results of this review will never stand alone, but will be compared to the standard review. The cloud based software for AI-assisted review, are hosted on approved secure servers within the European Union and in compliance with current legislation for handling of personal data. Videos used in the analysis are created without identifiers and are deleted after review.

Hence, we believe no increased risk is associated with participation in this study. Participants are covered by *Patienterstatningen*.

## Ethical considerations

This study is conducted in accordance with the guidelines for biomedical research involving human subjects outlined by the *Declaration of Helsinki* and after approval from the Regional Ethics Committee for Southern Denmark.

Patients are recruited from medical gastroenterology units at public hospitals in the Region of Southern Denmark. Patients are informed orally by the treating physician and in writing and offered time for reflection before signing the declaration of consent. The patient is offered another consultation if he or she needs a lay representative. Patients may at any time withdraw their consent to participate in the study without it impacting the treatment they otherwise receive in the gastroenterology outpatient clinics.

Imaging modalities selected for this study are all – except IC – minimally invasive, patient friendly and without use of ionizing radiation. IC is indicated as first line diagnostic procedure if patients reject participation in this study. We anticipate that rare cases of malignancy will be detected irrespective of the diagnostic modalities performed. We believe no increased risk is associated with participation in this study. We believe the additional AI-assisted review will pose no risk to the patients. On the contrary, previous studies have shown that AI systems find more pathology than standard analysis by an experienced physician, and any disagreement will be reviewed by an expert. Our study examines whether a minimally invasive diagnostic strategy is non-inferior to traditional diagnosis using IC as first line procedure. Possibly, IC can be avoided in the future for the initial diagnosis of patients with suspected CD. In addition, only one diagnostic procedure will be required to visualize CD in both the colon and the small intestine compared to two or more examinations performed today.

At any time during the study, a patient can be withdrawn from the study by the treating gastroenterologist if indicated. Additional examinations and medical treatment can be performed without restrictions. Thus, neither diagnosis nor treatment of the patient will be compromised by participation in this study.

Current guidelines do not recommend routine use of a patency capsule prior to CE to prevent capsule retention in patients with suspected CD. In the present study, pan-enteric CE is preceded by a thorough clinical assessment, supplemented with the patency capsule system if deemed necessary. This almost eliminates the risk of capsule retention. In patients examined with IUS or MRE, the radiologist has to inform the primary investigator if one or more of the following findings are identified:

- Small bowel stenosis
- Abscess or fistula

- Subileus or ileus
- Suspected malignancy
- Other intra-abdominal conditions requiring acute or subacute intervention

## **Approval**

The study will be initiated after approval by the Regional Ethics Committee for Southern Denmark and listed on the trial register of the Region of Southern Denmark and the ClinicalTrials.gov database. All patients will give informed consent before participation, and the study is conducted within the requirements of the Danish law. Collaborations with national and foreign research institutions is conducted in agreement with the General Data Protection Regulation (GDPR).

## **Privacy**

Patients will sign written informed consent before participation, and the study is conducted within the requirements of the Danish Data Protection Act (DDPA). Clinical data are prospectively collected after informed consent has been declared with the exceptions noted in the following section, and personal information will not be passed to persons without connection to the study. For collaborations with other research institutions, images / videos are anonymized. No personal data or person identifiable information will be shown (e.g. faces). For analysis in the AI based software, images are considered pseudo-anonymized data, and data processing agreements are made to ensure data safety, compliance with legislation and privacy of the participants. Apart from the anonymized images / videos, no clinical or person identifiable information is passed on to external partners, and data will not be stored externally after AI review. Only doctors involved in this project have access to these data. The primary investigator or sub-investigators at participating centers will obtain a medical history, perform a physical examination, and he is informed about the results of pan-enteric CE, IC, histopathology and MRE. These data will be stored at a secure server under OPEN SDU. Furthermore, digital copies of pan-enteric CEs and videos from the ICs will be sent to the primary investigator for subsequent analysis. MR images are saved digitally on the local and regional picture archiving and communications system (PACS), and images are accessible for central review by the participating radiologist at Department of Radiology, Lillebaelt Hospital. Results of pan-enteric CE, IC and MRE are reported in a standardized fashion and sent to the treating gastroenterologist.

## **Information from medical records**

*Transmission without consent*

Before the patient has signed the declaration of consent, information including personal data from referrals to participating centers will be passed on to the investigators in order to determine eligibility for inclusion as per the in- and exclusion criteria mentioned above. Referrals marked with a diagnosis code listed in appendix 1 can be passed on to the investigators. Personal data passed on comprises name, Central Personal Register (CPR) number, and the referral text which may include symptoms, physical findings, medications, preexisting conditions, and results from previously performed biochemical and imaging examinations. We expect to screen 330 referrals during the inclusion period from September 1st 2024 to April 1st 2027.

#### *Transmission with consent*

The following data are collected by interview and review of the medical records:

- Demographic, socioeconomic and clinical characteristics
- Diagnosis and disease classification
- Patient satisfaction after diagnostic procedures
- Disease activity (Simple Clinical Colitis Activity Index and Harvey-Bradshaw index)
- Biochemistry including fecal calprotectin
- Endoscopic procedures
- Result of histology
- Imaging procedures
- Medical treatments
- Visits at the outpatient clinic, general practitioner or nurse including time for preparation for endoscopic procedures
- Hospital admissions
- Surgery
- Sick leave

Data regarding demographic, socioeconomic and clinical characteristics are necessary to evaluate the results of most endpoints and identify previously unrecognized differences in the study results across randomization arms. Diagnosis and disease classification, information on medical treatments as well as results from endoscopic procedures, histology, and imaging procedures are necessary to determine the main endpoint of the study, evaluate differences in disease classification and medical treatments between randomization arms and determine expenditures. Data on hospital admissions and sick leave are necessary to determine expenditures and loss of productivity.

By providing consent, the patient allows the investigators and regulatory authorities direct access to information in the patient's medical records, including electronic records, in order to view information about the patient's health status, which is necessary for the conduct of the research project and for control purposes, including self-inspection, quality control and monitoring, which they are obliged to carry out.

